### **5.3.2. Alcohol, Caffeine and Tobacco**

- Intake of alcohol is permitted in moderation (refer to exclusion criterion [20](#) for acceptable amount of alcohol consumption).
- Caffeine containing products will be permitted during the study with the following restrictions: caffeine containing products may not be consumed within 1 hour prior to measuring vital signs and ECGs.
- Use of nicotine-containing products is permitted in this study with the following restrictions: nicotine-containing products may not be used within 1 hour prior to measuring vital signs and ECGs.

### **5.3.3. Physical Activity**

Participants will not be permitted to perform physically strenuous exercise (for example: heavy lifting, weight training, calisthenics and aerobics) within 48 hours prior to blood sample collections; walking at a normal pace is permitted.

### **5.3.4. Contraception**

The investigator or his or her designee, in consultation with the participant, will confirm that female participants have selected an appropriate method of contraception from the permitted list of contraception methods (see [Appendix 4, Section 10.4.4](#)) and will confirm that the participant has been instructed in its consistent and correct use. At time points indicated in the [SoA](#) the investigator or designee will inform the participant of the need to use highly effective contraception consistently and correctly and document the conversation and the participant's affirmation in the participant's chart (participants need to affirm their consistent and correct use of at least 1 of the selected methods of contraception). In addition, the investigator or designee will instruct the participant to call immediately if the selected contraception method is discontinued or if pregnancy is known or suspected in the participant or partner.

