## 1.2. Schema

### 1.3. Schedule of Activities (SoA)

The SoA table provides an overview of the protocol visits and procedures. Refer to the [STUDY ASSESSMENTS AND PROCEDURES](#) section of the protocol for detailed information on each procedure and assessment required for compliance with the protocol. The investigator may schedule visits (unplanned visits) in addition to those listed in the SoA table, in order to conduct evaluations or assessments required to protect the well-being of the participant.

Protocol Activity (See Appendix 10 for abbreviations)	Screen	Pbo Run- In	Treatment Phase						End of Treatment	Follow Up		Early Termination
			0	2	4	6	8	12		16	17- 18	
Weeks Relative to Dosing on Day 1			0	2	4	6	8	12	16	17- 18	20- 21	ET
Days Relative to Dosing on Day 1	-42 to 15	-14±3	1	14±3	28±3	42±3	56±3	84±3	112±3	119- 126	140- 147 a	
Visit	V1	V2	V3	V4	V5	V6	V7	V8	V9	V10	V11	
Informed consent & demography	x											
Review of eligibility criteria	x	x	x									
Open-ended inquiry for adverse events	x	→	→	→	→	→	→	→	→	→	x	x
Medical history	x											
Review prior or concomitant treatments	x	→	→	→	→	→	→	→	→	→	x	x
Review drug, alcohol/tobacco use	x	→	→	→	→	→	→	→	→	→	x	x
Review contraception use (females only)	x	→	→	→	→	→	→	→	→	→	x	x
Counseling on diet/exercise guidelines		x										
Dispense glucometer and supplies, drug diary, glucose log & provide training		x										
Review drug diary, glucometer & glucose log			x	x	x	x	x	x	x	x		x
Glucose measurement (fasting, via glucometer, on site)		x	x	x	x	x	x	x	x	x		
Physical examination (height at Screen only) b	x		x						x	x		x
Supine vital signs	x	x	x c	x	x c	x	x c	x	x c	x		x
Supine 12 lead ECG	x		x c	x	x c	x	x c	x	x c	x		x
Body weight (in duplicate) d	x	x	x	x	x	x	x	x	x	x		x
Registration in trial (via IRT)	x											
Randomization in trial (via IRT)			x									
Dispensation of IP		x e	x f	x f	x f	x f	x f	x f	x f			

Protocol Activity (See Appendix 10 for abbreviations)	Screen	Pbo Run- In	Treatment Phase						End of Treatment	Follow Up		Early Termination
			0	2	4	6	8	12		16	17- 18	
Weeks Relative to Dosing on Day 1			0	2	4	6	8	12	16	17- 18	20- 21	ET
Days Relative to Dosing on Day 1	-42 to 15	-14±3	1	14±3	28±3	42±3	56±3	84±3	112±3	119- 126	140- 147 a	

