Visit	V1	V2	V3	V4	V5	V6	V7	V8	V9	V10	V11	
Dosing on site of IP (with food)		x	x	x	x	x	x	x	x			
IP/Placebo-run in compliance			x	x	x	x	x	x	x			x
Blood Sampling for:												
Fasting plasma glucose and HbA1c	x	x	x	x	x	x	x	x	x	x		x
Hematology, chemistry (inc. eGFR)	x		x	x	x	x	x	x	x	x		x
FSH (females only), C-peptide	x											
Pregnancy test (females only)	x	x	x	x	x	x	x	x	x	x		x
Lipids, TSH, free T4, calcitonin, amylase, lipase, TBA, PT/INR/aPTT, CCI	x		x		x		x	x	x	x		x
CCI												
Urine Sampling for:												
Urine drug test	x											
Urinalysis (and microscopy, if appropriate)	x		x		x		x	x	x	x		x
On-site urine pregnancy test (females only) i		x	x	x	x	x	x	x	x	x		x
a. Visit may be a phone call. b. Full physical examination performed according to the SoA. A limited physical examination is performed at the follow up visit and may be performed at non-specified visits if there are findings during the previous exam or new/open AEs, if appropriate and at investigator discretion. c. Measured in triplicate pre-dose (V3, V5, V7, and V9) and post-dose ( only V5, V7, and V9). d. The second weight measurement should be obtained at least 1-2 minutes apart from the first weight measurement. e. On V2 only, IP reflects single blinded placebo. f. For V3 through V8, IP is dispensed via IRT and reflects double-blind randomized PF-06882961 or placebo. g. [Redacted] h. [Redacted] i. For V2 through V9, the test result must be reviewed and deemed acceptable (ie, negative), in order to continue participation in the study.												

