### **10.4.2. Female Participant Reproductive Inclusion Criteria**

A female participant is eligible to participate if she is not pregnant or breastfeeding, and at least 1 of the following conditions applies:

- Is not a woman of child bearing potential (WOCBP) (see definitions below in [Section 10.4.3](#)).

OR

- Is a WOCBP and using a contraceptive method that is highly effective (with a failure rate of  $<1\%$  per year), preferably with low user dependency, as described below during the intervention period and for at least 28 days after the last dose of study intervention, which corresponds to the time needed to eliminate any reproductive safety risk of the study intervention(s). The investigator should evaluate the effectiveness of the contraceptive method in relationship to the first dose of study intervention.
- Is a WOCBP and using a contraceptive method that is highly effective (with a failure rate of  $<1\%$  per year), with high user dependency, as described below during the intervention period and for at least 28 days after the last dose of study intervention, which corresponds to the time needed to eliminate any reproductive safety risk of the study intervention(s). In addition, a second effective method of contraception, as described below, must be used. The investigator should evaluate the effectiveness of the contraceptive method in relationship to the first dose of study intervention.

The investigator is responsible for review of medical history, menstrual history, and recent sexual activity to decrease the risk for inclusion of a woman with an early undetected pregnancy.

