#### **10.4.4. Contraception Methods**

##### **Highly Effective Methods That Have Low User Dependency**

1. Implantable progestogen-only hormone contraception associated with inhibition of ovulation.
2. Intrauterine device (IUD).
3. Intrauterine hormone-releasing system (IUS).
4. Bilateral tubal occlusion.
5. Vasectomized partner.

- Vasectomized partner is a highly effective contraceptive method provided that the partner is the sole sexual partner of the WOCBP and the absence of sperm has been confirmed. If not, an additional highly effective method of contraception should be used. The spermatogenesis cycle is approximately 90 days.

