### **Highly Effective Methods That Are User Dependent**

1. Combined (estrogen- and progestogen-containing) hormonal contraception associated with inhibition of ovulation:
  - oral;
  - intravaginal;
  - transdermal;
  - injectable.
2. Progestogen-only hormone contraception associated with inhibition of ovulation:
  - oral;
  - injectable.
3. Sexual abstinence:
  - Sexual abstinence is considered a highly effective method only if defined as refraining from heterosexual intercourse during the entire period of risk associated with the study intervention. The reliability of sexual abstinence needs to be evaluated in relation to the duration of the study and the preferred and usual lifestyle of the participant.

One of the following effective barrier methods must be used in addition to the highly effective methods listed above that are user dependent:

- Male or female condom with or without spermicide;
- Cervical cap, diaphragm, or sponge with spermicide;
- A combination of male condom with either cervical cap, diaphragm, or sponge with spermicide (double-barrier methods).

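### Section 5.3.4 has women affirm only one contraceptive method at each visit, although Appendix 4 requires two for those on a user-dependent method

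*Protocol*

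**What the plan says.** Three parts of the protocol bear on this point.

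- **The rule (Appendix 4).** For a woman of childbearing potential whose highly effective method is highly user dependent, Section 10.4.2 says: "In addition, a second effective method of contraception, as described below, must be used". Section 10.4.4 says what the second method is: "One of the following effective barrier methods must be used in addition to the highly effective methods listed above that are user dependent". The requirement covers the intervention period and at least 28 days after the last dose. The separate list headed "Highly Effective Methods That Have Low User Dependency" carries no general second-method requirement.
- **The on-study check (Section 5.3.4).** At the Schedule of Activities (SoA) time points, "the investigator or designee will inform the participant of the need to use highly effective contraception consistently and correctly". The conversation and her affirmation go in the chart, and the content of the affirmation is defined in a parenthesis: "participants need to affirm their consistent and correct use of at least 1 of the selected methods of contraception". The site must also "instruct the participant to call immediately if the selected contraception method is discontinued".
- **The schedule (Section 1.3).** A row for review of contraception use in females runs from V1 to V11 and early termination, without saying what the review must cover. Pregnancy tests are scheduled from V1 to V10 and at early termination. Footnote i says of the on-site urine test: "For V2 through V9, the test result must be reviewed and deemed acceptable (ie, negative), in order to continue participation in the study".

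**The concern.** For women who must use two methods, the documented standard is weaker than the rule it supports. A participant on an oral contraceptive who has stopped using condoms can truthfully affirm one method. The site can then chart compliance with Section 5.3.4 while she is in breach of Section 10.4.2. Read literally, the same holds if she stops the pill and affirms only the condom, although the surrounding reference to highly effective contraception makes that case easier to catch.

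Section 4.2 explains why contraception is monitored: marketed drugs of this class are contraindicated in pregnancy, and the protocol undertakes to limit the risk of pregnancy among enrolled women. What is at stake is whether a lapse in a required method is found before a pregnancy occurs. No efficacy or safety analysis depends on it.

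**Working it through.** The check is mainly a comparison of texts, with a short calculation to bound the consequence.

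**1. Does a breach of Appendix 4 fail the Section 5.3.4 affirmation?**

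| Participant | Methods required (10.4.2, 10.4.4) | Methods to affirm (5.3.4) | Match? |
|---|---|---|---|
| Low-user-dependency method | 1 | at least 1 | yes |
| User-dependent method | 2 (method plus barrier) | at least 1 | no |

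In the second row, a woman using one of two required methods is non-compliant with Appendix 4 and compliant with the affirmation.

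**2. Does other text close the gap?**

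- The SoA review row names the activity only. Section 5.3.4 is the only visible text that says what the affirmation must contain.
- The call-in instruction relies on the participant to report, and it is worded for a single method.
- Pregnancy tests (SoA, Section 8.2.7) detect a pregnancy, not a lapsed method. They limit how long a fetal exposure could last.
- Concomitant-treatment questioning (Section 6.5) can reveal a stopped hormonal drug, but not a dropped barrier or lapsed abstinence.

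None of these requires the site to ask about both methods.

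**3. How large is the consequence?**

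- Required period: 16 weeks of dosing plus 28 days = 16 × 7 + 28 = 140 days (20 weeks).
- Class failure rate for a highly effective method (10.4.2): under 1% per year.
- Risk over 140 days if only the barrier is dropped: 1% × 140/365 = 0.38%. Compounded, 1 − 0.99^(140/365) = 0.385%. Either way it is below about 0.4% per woman.

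This bounds her total pregnancy risk on the remaining method. It is not the increment from losing the barrier, for which the documents give no basis. It also assumes that the class rate holds for a user-dependent method used alone, whereas Appendix 4 requires a second method in exactly that case. It does not apply to a woman who keeps only the barrier.

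**4. Where does the review of contraception carry most weight?**

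As the SoA table reads, the last scheduled pregnancy test is at V10 (Day 119 to 126). The 28 days after nominal Day 112 end on Day 140, so 140 − 126 = 14 to 140 − 119 = 21 days remain. The next scheduled check is the V11 review, which may be a phone call. Section 8.2.7 mentions a test at the end of the study, but the SoA shows none at V11.

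**The case against.** The strongest reply is that this is a drafting slip with little practical effect.

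- **Appendix 4 still binds.** The parenthesis in 5.3.4 sets a documentation minimum and does not permit a woman to stop a required method. A careful site reviewing contraception against Appendix 4 would ask about both. This stands, but it relies on sites doing more than the text asks.
- **Section 6.5 provides another route.** Participants are questioned about concomitant treatment at each clinic visit, and start and stop dates are recorded. Most user-dependent methods are hormonal drugs, so stopping one should come to light. This stands for the riskier lapse, in which the hormonal method is stopped and only a barrier remains. It does not reach a dropped barrier or lapsed abstinence.
- **The remaining risk is low.** A woman who drops only the barrier keeps a method classed as highly effective, must test negative to continue at V2 to V9, and stops study drug if pregnancy is confirmed. Embryo-fetal studies were completed in two species. All of this stands and limits the severity.
- **The singular in the call-in instruction is read too literally.** A woman who stops either method has stopped a selected method. That is a fair reading, but the wording still leaves it to her to see it that way.
- **The V10 to V11 interval is a separate matter.** The proposed wording adds no test. The interval shows only where the conversation matters most; it is not part of the defect.

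These points bear on how much the mismatch matters. They do not remove it.

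**Conclusion.** The concern holds. For women of childbearing potential on a user-dependent method, Section 5.3.4 states a standard that a participant can meet while breaching Sections 10.4.2 and 10.4.4, and no visible text requires both methods to be confirmed. For women on a low-user-dependency method the wording is correct.

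The safety effect is small: below about 0.4% per woman over 140 days if only the barrier is lost, assuming the class rate of under 1% per year applies. The total effect cannot be estimated because the documents do not give the number of women in the subgroup. There is no effect on the statistical analysis. The correction should be made because it changes what sites must elicit and chart, but it does not threaten the trial's conclusions.

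**What to change.** Make two wording changes in Section 5.3.4.

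1. Replace the one-method minimum in the affirmation with all methods of contraception required for that participant under Section 10.4.4, stating that this means both methods where a user-dependent method is used.
2. Reword the call-in instruction so that she calls if any required method is stopped.

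Women on a low-user-dependency method would still affirm one method. The cost is two phrases in the protocol and an update to any site source form that repeats them, with no extra visits, tests or analyses. Monitors would then have one standard for judging a deviation.

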## **5.4. Screen Failures**

Screen failures are defined as participants who consent to participate in the clinical study but are not subsequently randomly assigned to IP. A minimal set of screen failure information is required to ensure transparent reporting of screen failure participants to meet the Consolidated Standards of Reporting Trials (CONSORT) publishing requirements and to respond to queries from regulatory authorities. Minimal information includes demography, screen failure details, eligibility criteria, and any SAE.

A participant who qualified for this study but did not enroll within the protocol prescribed screening period may be re-screened. All screening procedures must be repeated, and the participant assigned a new 8-digit study-specific subject identification (SSID) number.

## 6. STUDY INTERVENTION

Study intervention is defined as any investigational intervention(s), marketed product(s), placebo, or medical device(s) intended to be administered to a study participant according to the study protocol.

For the purposes of this protocol, the term IP may be used synonymously with study intervention. For this study, the IP is PF-06882961 and matching placebo tablets; and will be administered orally BID with food.

Treatment Phase IP will be packaged in blister cards containing blinded PF-06882961 or matching placebo for oral administration. Treatment assignment will be blinded, and blister cards will be labeled according to local regulatory requirements. For the placebo run-in, placebo tablets will be packaged in blister cards according to local regulatory requirements.

For participants taking metformin, they will continue taking their own metformin medication at the same total daily dose that was prescribed prior to study entry, except in circumstances where a dose change is deemed medically necessary.

### 6.1. Study Intervention(s) Administered

Intervention Name	PF-06882961	Placebo for PF-06882961
ARM Name	Active	Placebo
Type	Drug	Drug
Dose Formulation	Tablet	Tablet
Unit Dose Strengths	2.5 mg, 10 mg, 40 mg and 100 mg	Not applicable
Target Dosage Levels (achieved upon titration)	2.5, 10, 40, 80, 120 mg BID	0 mg BID
Route of Administration	Oral	Oral
Sourcing	Provided centrally by the sponsor. Refer to the Investigational Product Manual.	Provided centrally by the sponsor. Refer to the Investigational Product Manual.
Packaging and Labeling	Study intervention will be provided in blister packs. Each blister pack will be labeled as required per country requirement.  Blinded labels will be utilized for placebo run-in, titration and stable dosing blister packs.	Study intervention will be provided in blister packs. Each blister pack will be labeled as required per country requirement.  Blinded labels will be utilized for placebo run-in, titration and stable dosing blister packs.

Participants will take 4 tablets of IP (PF-06882961 or matching placebo) in the morning with food and 4 tablets of IP in the evening with food, for a total of 8 tablets of IP daily. Participants will swallow the IP whole, and will not crush, chew, break, or dissolve the IP prior to swallowing. The same dosing paradigm will be used during the placebo run-in period.

The morning and evening doses should be taken approximately 10-12 hours apart and at approximately the same time each day. Participants should be instructed that if they forget to take a dose at their usual time, they should take that dose as soon as possible (with food), ensuring that there is at least an 8-hour interval between that dose and the next dose. If the interval to the next dose is less than 8 hours, then the dose should not be administered.

Dosing and administration instructions along with a dosing diary, will be provided to participants to support at home dosing of IP. When participants self-administer the IP at home, they will record each dose, including date and time, in the dosing diary.

Morning dosing will occur with food at the site at V2-V9. Participants will be instructed to arrive at the site in the fasted state, bring their IP with them, and to delay self-administration of IP on scheduled visit days until they arrive for their clinic visit. When participants dose at the site, they will self-administer the IP under supervision by study staff. The date and time of each dose administered at the site will be recorded in the site source documents and in the dosing diary. CCI

Titration and dosing schemes for target doses are provided below; additional details regarding titration are provided in the IP Manual.

**Table 2. Titration and Dosing Scheme**

Target Dose (mg) BID	Week 1	2	3	4	5	6	7	8	9	10	11	12	13	14	15	16
	Titration Phase						Stable Dose Phase									
2.5	2.5	2.5	2.5	2.5	2.5	2.5	2.5	2.5	2.5	2.5	2.5	2.5	2.5	2.5	2.5	2.5
10	10	10	10	10	10	10	10	10	10	10	10	10	10	10	10	10
40	10	20	40	40	40	40	40	40	40	40	40	40	40	40	40	40
80	10	20	40	60	80	80	80	80	80	80	80	80	80	80	80	80
120	10	20	40	60	80	100	120	120	120	120	120	120	120	120	120	120
Placebo	0	0	0	0	0	0	0	0	0	0	0	0	0	0	0	0

**6.2. Preparation/Handling/Storage/Accountability**

1. The investigator or designee must confirm appropriate temperature conditions have been maintained during transit for all study interventions received and any discrepancies are reported and resolved before use of the study intervention, as applicable for temperature-monitored shipments.
2. Only participants enrolled in the study may receive study intervention and only authorized site staff may supply or administer study intervention. All study interventions must be stored in a secure, environmentally controlled, and monitored (manual or automated recording) area in accordance with the labeled storage conditions with access limited to the investigator and authorized site staff. At a minimum, daily minimum and maximum temperatures for all site storage locations

- must be documented and available upon request. Data for nonworking days must indicate the minimum and maximum temperature since previously documented for all site storage locations upon return to business.
3. The investigator, institution, or the head of the medical institution (where applicable) is responsible for study intervention accountability, reconciliation, and record maintenance (ie, receipt, reconciliation, and final disposition records). All study interventions will be accounted for using an IP accountability form/record. All IP that is taken home by the participant, both used and unused, must be returned to the investigator by the participant.
  4. Further guidance and information for the final disposition of unused study interventions are provided in the IP manual.
  5. Any storage conditions stated in the SRSD will be superseded by the storage conditions stated on the product label.
  6. Study interventions should be stored in their original containers and in accordance with the labels.
  7. Site staff will instruct participants on the proper storage requirements for take-home study intervention.
  8. Any excursions from the study intervention label storage conditions should be reported to Pfizer upon discovery along with any actions taken. The site should actively pursue options for returning the study intervention to the storage conditions described in the labeling, as soon as possible. Once an excursion is identified, the study intervention must be quarantined and not used until Pfizer provides permission to use the study intervention. It will not be considered a protocol deviation if Pfizer approves the use of the study intervention after the temperature excursion. Use of the study intervention prior to Pfizer approval will be considered a protocol deviation. Specific details regarding the definition of an excursion and information the site should report for each excursion will be provided to the site in the IP manual.
  9. The sponsor or designee will provide guidance on the destruction of unused study intervention (eg, at the site). If destruction is authorized to take place at the investigator site, the investigator must ensure that the materials are destroyed in compliance with applicable environmental regulations, institutional policy, and any special instructions provided by Pfizer, and all destruction must be adequately documented.

Additional details about accountability, storage, destruction, and excursion reporting can be found in the IP manual.

